10.4 Final Analysis Plan

We will assessCOVID-19-free survival in high-risk healthcare workers who receive hydroxychloroquine compared to those who receive placebo.

We will compare survival in a time-to-event analysis for COVID-19-free survival using Log-rank test with survival displayed as a Kaplan-Meier curve. Analysis will be intention-to-treat. Persons who develop confirmed COVID-19 or die will be considered failures. Persons lost to follow up will be censored.

Secondary endpoints for incidence will be assessed via Fisher's Exact test for the proportions by study arm. The secondary endpoint on the ordinal scale will be assessed with a proportional odds model.

PREP COVID-19

Version 1.0 27 March 2020

Among those with symptoms, severity of symptoms (recorded on a 0-10 visual analog scale) will be compared via Mann-Whitney U by study arm.

A priori subgroup analyses will include assessment by:

- Days from Exposure
- Decile of age
- Sex as a biological variable
- Censored subjects, who became symptomatic before receipt of the first dose of study medicine, will be separately analyzed and reported.

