4.1 DESIGN

Randomized, double-blind clinical trial, parallel design. This is an event-driven trial. Subjects will be followed until study termination. Study drug will be prescribed for up to 12 weeks.

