7.2 Laboratory Evaluations

There are no laboratory evaluations in the protocol. There is an opportunity for participants to participate in an optional lab-based sub-study. Details in Appendix A.

Clinical outcomes are by self-report.

SARS-COV2 positivity is by self-report.

Informed consent will request permission to contact local public health authorities or their medical provider in the event of loss to follow up or COVID-19 disease. Public health authorities or medical providers may verify confirmatory laboratory results.

There is no incentive to be dishonest, and we believe healthcare workers in particular will take their responsibilities seriously.

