10.2 Sample Size Considerations

The planned sample size is up to 3500 participants. There will be two comparisons: treatment once weekly compared to placebo, and treatment twice weekly compared to placebo. With 1165 participants in each of the two treatment groups and in one placebo group, a two-sided log-rank test achieves 80% power at alpha = 0.025 significance level to detect a hazard ratio of 0.65 when COVID-19 free survival is 90% in the placebo group.

The study is powered at alpha = 0.025 to account for the two treatment versus placebo comparisons. The two treatment groups will be compared to the same placebo group. Assumed loss to follow-up is 5% in the treatment groups and 15% in the placebo group. With 3500 participants approximately 310 COVID-19 or death events are anticipated.

Sample Size Re-estimation:

At the time of the second DSMB review, a sample size re-estimation will occur based on the disease transmission rate in the control group. The conservative *a priori* assumption (based on limited data) is 10% transmission risk. The table below shows that if the transmission rate is 8% (lower than assumed) then the sample size would need to be increased to a total of 4353 participants. On the other hand, if the transmission rate is greater than the assumed 10% then the sample size can be decreased.

Sample size requirements to detect a hazard ratio of 0.65 based on COVID19 transmission rates without treatment (assuming 80% power, alpha = 0.025, 15% loss to follow-up in the placebo group and 5% loss to follow-up in the treatment groups)

COVID 19 Transmission Rate Without Treatment	Number Per Group	Total Sample Size (3 Groups)
8%	1451	4353
10%	1163	3489
12%	971	2913
15%	778	2334
18%	650	1950
20%	580	1740

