10.3 Planned Interim Analyses

Interim analyses will focus on the statistical testing of the primary endpoint with descriptive reporting of the secondary endpoints as well. Interim analyses will be conducted after enrollment of approximately: 25%, 50%, 75%, and 100% of participants are enrolled. This interval may be modified by the DSMB.

A Lan-DeMets spending function analog of the O'Brien-Fleming boundaries will be used for the outcome of COVID-19-free survival. The provided table assumes four interim analyses with the final analysis with an overall alpha=0.025. The boundaries are truncated at |Z| = 3.01.

Interim Analysis	Sample Size	Z	P-value
1	~875 (25%)	> 3.1	.0019
2	~1750 (50%)	> 3.1	.0036
3	~2625 (75%)	> 2.78	.0179
Final	3500 (100%)	> 2.30	.025

Should a stopping boundary be crossed, we would recommend an analysis to determine whether the findings are consistent across secondary endpoints, such that a clear answer is achieved. In the event of early halting due to efficacy, the study will immediately convert to an open-label observational cohort of hydroxychloroquine prescribed to all consented participants.

Based on the public health situation, the DSMB has the prerogative to alter the stopping rules.

Futility Analysis:

If the conditional power is <20% at the time of the second interim analysis with approximately 50% of participants enrolled, discontinuation should be considered as a possible recommendation by the DSMB. The sample size re-estimation will be considered here as well as the pace of enrollment.

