11 SOURCE DOCUMENTS AND ACCESS TO SOURCE DATA/DOCUMENTS

Source documents will include internet forms self-completed by participants directly entered into a RedCAP database.

This protocol is based on self-report.

This internet-based protocol is meant to enable a large number of participants to be recruited quickly as well as maintain the safety of the research staff. In-person visits may cause delays, compliance issues, and public health concerns. The internet-based design allows us to rapidly enroll participants across the country, in the setting of a public health emergency.

Participants will be asked to provide consent to obtain medical records from their healthcare provider or public health official, if there is the need to verify outcomes, for SARS-CoV-2 test results or hospitalizations.

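### Fisher tests of the secondary incidence endpoints cannot use the primary's censoring, so under the plan's assumed 15% v 5% loss their result depends on an unstated rule

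*Combined protocol and SAP*

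**What the plan says.** Section 10.4 analyses COVID-19-free survival by log-rank test. It states "Analysis will be intention-to-treat" and, for the primary, "Persons lost to follow up will be censored". Its next paragraph gives the secondary incidence endpoints Fisher's "Exact test for the proportions by study arm. The secondary endpoint on the ordinal scale will be assessed with a proportional odds model". No denominator is given, and nothing says whether a lost participant is excluded, a non-event or an event.

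Section 10.2 expects unequal loss: "Assumed loss to follow-up is 5% in the treatment groups and 15% in the placebo group". Follow-up also varies between people. Section 4.1 says "Subjects will be followed until study termination", and the Summary gives a minimum of 4 weeks.

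Three other places bear on the point:
- Section 5.3.4 counts withdrawals as failures, but only for completion of study medication.
- Section 7.2 has the consent form ask for "permission to contact local public health authorities or their medical provider in the event of loss to follow up" or of COVID-19 disease. Section 11 seeks access to records "if there is the need to verify outcomes, for SARS-CoV-2 test results or hospitalizations". Neither sets an analysis rule.
- Section 10.3, after a stopping boundary is crossed, recommends an analysis to "determine whether the findings are consistent across secondary endpoints, such that a clear answer is achieved".

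On severity, Section 3.2.2 restricts the ordinal scale to people who develop COVID-19, yet its first level is no illness. Section 10.4 compares a 0-10 symptom score among symptomatic participants only. Section 10.1 states milder disease among treated cases as a hypothesis.

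**The concern.** Intention-to-treat fixes who belongs to each arm. It does not say what outcome a lost person has. The log-rank test deals with that by censoring, but a proportion has to count the person one way or another. When loss differs by arm, each obvious way can move the comparison even if the drug does nothing.

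Confirmed detection overlaps the primary, so the two could disagree through loss handling alone. Possible COVID-19 is the most exposed endpoint, because symptoms are less likely than tests or admissions to be recovered from records. Variable follow-up adds a smaller problem: a crude proportion refers to no fixed time. Randomisation balances planned follow-up between arms, so this makes the estimate harder to interpret but does not bias it.

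The severity comparisons raise a separate issue. Restricting to cases, or to people with symptoms, conditions on something the drug may change.

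**Working it through.** The plan gives no figure for these secondary analyses, so there is none to reproduce.

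**Inputs from Section 10.2:** 1165 per arm; 10% placebo risk; hazard ratio (HR) 0.65, so treated risk = 1 − 0.90^0.65 = 6.62%; loss 15% v 5%.

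**Assumptions:** the secondary endpoint has the primary's 10% risk; loss is independent of outcome; no lost outcome is retrieved; two-sided 0.025 is illustrative, since the plan assigns no level to secondaries. Timing of loss is not given, so two patterns bracket it: spread at a constant rate over follow-up, and all at day 0.

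**Expected proportions, spread loss, no drug effect.** Take follow-up as one unit of time.
- Event hazard λ = −ln 0.90 = 0.1054. Loss hazard γ = −ln 0.85 = 0.1625 (placebo) and −ln 0.95 = 0.0513 (treatment).
- Event seen before loss: q = λ/(λ+γ) × [1 − e^−(λ+γ)].
- Placebo: 0.1054/0.2679 × (1 − 0.90×0.85) = 0.3934 × 0.235 = 9.24%.
- Treatment: 0.1054/0.1567 × (1 − 0.90×0.95) = 0.6726 × 0.145 = 9.75%.
- Lost as non-events: risk ratio (RR) = 9.75/9.24 = 1.055.
- Lost excluded: q/(q + those event-free and not lost). Placebo 0.0924/(0.0924 + 0.765) = 10.78%; treatment 0.0975/(0.0975 + 0.855) = 10.24%; RR = 0.95. Exclusion keeps events that precede loss and drops the event-free time of the lost, so it inflates risk more where loss is higher.

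**Day-0 loss, no drug effect.** Lost as non-events: 0.85×10% = 8.5% v 0.95×10% = 9.5%, RR 1.12. Lost excluded: 10% v 10%, RR 1.00, on about 990 and 1107 people.

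**Rejection and power.** Fisher figures are by exact enumeration and log-rank figures by simulation. Each cell shows spread loss, then day-0 loss.

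| Analysis | RR, no effect | Rejection, no effect | Power, HR 0.65 |
|---|---|---|---|
| Fisher, lost as non-events | 1.06; 1.12 | 3.2%; 7.2% | 58%; 39% |
| Fisher, lost excluded | 0.95; 1.00 | 3.4%; 2.3% | 84%; 70% |
| Log-rank, censored | – | 2.6%; 2.4% | 74%; 72% |

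Without loss, Fisher rejects 2.1% under no effect and has 74% power. Under the non-event rule nearly all null rejections go against the drug (2.93 of 3.24 points for spread loss). Under exclusion with spread loss nearly all favour it: 0.37 of 3.4 points go against. The log-rank benchmark is below the plan's 80%; that is a separate sample-size matter and does not affect this comparison.

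**Disagreement at HR 0.65.** On identical events, log-rank rejects and Fisher does not in 16.5% (spread) or 32.5% (day 0) of trials under the non-event rule. Under exclusion the two tests differ in about 9% or 2%. Without loss the figure is 2.3%.

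**What shrinks it.** With half the lost outcomes retrieved under the non-event rule, null rejection is 2.4% to 3.2% and power 67% to 58%. With 10% v 5% spread loss, RR is 1.03 and power 66%. At a 2% risk, null rejection under the non-event rule is 1.9% to 2.4%, which does not exceed 2.5%.

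**Severity illustration.** Section 2.1 puts 14% + 6% = 20% of confirmed patients as severe or critical; treat that share as hospitalised (an assumption). Placebo cases: 1165×10% = 116.5, of whom 23.3 are hospitalised. Treated cases: 1165×6.62% = 77.1. If the drug prevents only outpatient cases, 23.3 are still hospitalised, so among cases the shares are 20% v 23.3/77.1 = 30%, although nobody was made worse. A case-only test then rejects 27% of the time. That falls to 7% to 9% if hospitalised cases are prevented half as much, and to 2.5% if prevention is equal.

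**The case against.** The strongest reply is that this is a missing sentence: state a denominator, trace the lost, and the gap closes. Part of that stands. Sections 7.2 and 11 foresee retrieval, and complete retrieval would remove the distortion from loss. At risks near 2%, which is about where hospitalisation or death falls in the illustration, there is little or no inflation. But choosing a denominator does not by itself solve the problem: with spread loss, both natural choices distort a true null, in opposite directions.

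A reader might infer more than the documents support:
- **That the secondaries are biased against the drug and lose power.** This follows only if the lost count as non-events. Section 10.4 does not say so; with exclusion and spread loss the bias runs the other way and power rises.
- **That no secondary rule exists, or that the failure rule for withdrawals extends to incidence.** Section 5.3.4 does give a rule, but for study-medication completion alone.
- **That a stopping decision would be misled.** Section 10.3 reports secondaries descriptively at interim looks, and its consistency check is a recommendation that does not require secondary significance. The disagreement rates above are for full-size tests and do not measure how often that check would go wrong.
- **That the case-only severity comparison is necessarily misleading.** The distortion arises only if prevention differs by severity, and the 27% is an extreme case. Because the scale lists no illness, even its population is not settled.

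**Conclusion.** The concern holds in this form: the direction and size of the distortion in the three secondary incidence endpoints depend on a rule that the plan does not state, and a Fisher test cannot use the censoring chosen for the primary. With no drug effect the risk ratio can lie anywhere from 0.95 to 1.12. At HR 0.65, power can lie anywhere from 39% to 84%, while the log-rank test stays near 72% to 74%. These ranges rest on the plan's 15% v 5% loss, a 10% risk, uninformative loss and no retrieval, and their day-0 ends are extremes. The documents give no risk for possible COVID-19, so its distortion cannot be sized directly. The primary analysis is unaffected. This is an inexpensive improvement worth making before unblinding.

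The severity point is secondary. Section 3.2.2 contradicts itself on who is on the ordinal scale, and comparisons among cases or symptomatic people should not carry a causal claim unaided.

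**What to change.** (a) Analyse confirmed detection, possible COVID-19, and hospitalisation or death in all randomised participants as time to first event, with a log-rank test and Kaplan-Meier risk, censored at last contact as for the primary. Apply retrieval of lost outcomes equally in all arms, and add a sensitivity analysis for informative loss. Keep Fisher for side effects and discontinuation, with a stated denominator consistent with Section 5.3.4.

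(b) Reconcile the ordinal scale's population with its no-illness level. Either analyse the scale in all randomised participants, or keep the case-only and symptomatic-only comparisons as descriptive. The second choice makes the conditional severity hypothesis in Section 10.1 descriptive too, and the plan should say so. In both cases read them beside the all-randomised hospitalisation-or-death endpoint.

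The cost is a few sentences and slightly more analysis work. Section 4.3.4 already queries symptoms, testing and hospitalisation weekly, so no new data are needed. The downsides are that confirmed detection will largely repeat the primary, and that hospitalisation or death will be imprecise, with about 23 events per arm in the illustration.

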11 SOURCE DOCUMENTS AND ACCESS TO SOURCE DATA/DOCUMENTS

Source documents will include internet forms self-completed by participants directly entered into a RedCAP database.

This protocol is based on self-report.

This internet-based protocol is meant to enable a large number of participants to be recruited quickly as well as maintain the safety of the research staff. In-person visits may cause delays, compliance issues, and public health concerns. The internet-based design allows us to rapidly enroll participants across the country, in the setting of a public health emergency.

Participants will be asked to provide consent to obtain medical records from their healthcare provider or public health official, if there is the need to verify outcomes, for SARS-CoV-2 test results or hospitalizations.

12 QUALITY CONTROL AND QUALITY ASSURANCE

Study medications will be FDA-approved following Good Manufacturing Practice.

13 ETHICS/PROTECTION OF HUMAN SUBJECTS

13.1 Ethical Standard

This study is to be conducted according to US and international standards of Good Clinical Practice (International Conference on Harmonization guidelines), Declaration of Helsinki, and International Ethical Guidelines for Biomedical Research Involving Human Subjects, applicable U.S. government regulations and institutional research policies and procedures. All investigators must have received human subject protection and GCP training prior to human subject involvement.

13.2 Institutional Review Board

Prior to the initiation of the study, the protocol, all informed consent forms and the participant Information materials will be submitted to and approved by the single IRB of record. Likewise, any future amendments to the study protocol will be submitted and approved by the IRB before implementation. This protocol and any amendments will undergo review and approval by the Human Subjects Board at the University of Minnesota under DHHS Assurance FWA00000312.

13.3 Informed Consent Process

- Written informed consent will be obtained via an English-language, internet-based web form. If potential participants have questions, they may contact [contact] to reach a study staff member to answer their questions about research, either via email or a phone call.
- After completion of reading the form, participants will be assessed for comprehension, querying:
 - Concept of Randomization to hydroxychloroquine (2 different doses) or vitamin placebo
 - Whether hydroxychloroquine is known to be effective in preventing disease
 - Duration of the study? (90 days)
 - Duration of taking the study medicine (12 weeks)
 - When follow up surveys will be sent (Days 1, weekly)
 - If hydroxychloroquine can be shared? (No)

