CRO	Contract Research Organization
DCC	Data Coordinating Center
DHHS	Department of Health and Human Services
DMID	Division of Microbiology and Infectious Diseases, NIAID, NIH
DSMB	Data and Safety Monitoring Board
eCRF	Electronic Case Report Form
FDA	Food and Drug Administration
FWA	Federalwide Assurance
GCP	Good Clinical Practice
HIPAA	Health Insurance Portability and Accountability Act
ICF	Informed Consent Form
ICH	International Conference on Harmonisation
IDS	Investigational Drug Services
IEC	Independent or Institutional Ethics Committee
IND	Investigational New Drug Application
IRB	Institutional Review Board
MERS-CoV	Middle East respiratory syndrome coronavirus

МОР	Manual of Procedures
Ν	Number (typically refers to subjects)
NIAID	National Institute of Allergy and Infectious Diseases, NIH
NIH	National Institutes of Health
OCRA	Office of Clinical Research Affairs, DMID, NIAID, NIH, DHHS
OHRP	Office for Human Research Protections
OHSR	Office for Human Subjects Research
ORA	Office of Regulatory Affairs, DMID, NIAID, NIH, DHHS
РНІ	Protected Health Information
PI	Principal Investigator
SAE	Serious Adverse Event
SOP	Standard Operating Procedure
US	United States
WHO	World Health Organization

[figure not shown]
Summary

Full Title:	Pre-exposure prophylaxis for coronavirus: A Pragmatic Randomized Clinical Trial	
Short Title:	PREP COVID-19	
Clinical Phase:	III	
Sponsor:	Investigator-Initiated Protocol, University of Minnesota	
Principal Investigators:	[name]	
Accrual Ceiling	3500	
Study Population	Healthcare workers at high risk for exposure to COVID-19 cases	
Objective	Test if pre-exposure prophylaxis with hydroxychloroquine can prevent development of COVID-19 disease	
Study Design	Double-blind, randomized clinical trial Internet-based trial driven by self-report. Study medicine delivered by courier to consented participants.	
Intervention Arms:	 Hydroxychloroquine 200mg tablet. 1. 400 mg orally once, followed by 400mg 6 to 8 hours later, thereafter 400mg weekly for the duration of follow up, up to 12 weeks 2. 400mg orally once, followed by 400mg 6 to 8 hours later, thereafter 400mg twice weekly for the duration of follow up, up to 12 weeks 	
Control Arm:	Placebo 2 tabs once, followed by 2 tabs 6 to 8 hours later, thereafter two tabs weekly or twice weekly for the duration of follow up, up to 12 weeks	
Primary Endpoint	COVID-19-free survival	

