Secondary Endpoints	 Incidence of confirmed SARS-CoV-2 detection Incidence of possible COVID19 symptoms Incidence of all-cause study medicine discontinuation Ordinal Scale of COVID-19 Disease maximum severity if COVID-19 diagnosed Incidence of Hospitalization for COVID-19 or death Incidence of study medication-related side effects 	
Duration of Participation	• Recruitment and follow up will be internet-based. All patients will be followed for at least 4 weeks. Recruitment is expected to take 4 weeks, for a total study duration of 8 weeks. But the total study duration will depend on the actual rate of enrollment. Study drug will be given for a maximum of 12 weeks.	
Inclusion Criteria	 Healthcare worker, at high risk of COVID-19 exposure: Persons primarily working in emergency departments (physicians, nurses, ancillary staff, triage personnel) Persons primarily working in intensive care units (physicians, nurses, ancillary staff, respiratory therapists) Persons performing aerosol generating procedures: ex. Anesthesiologists, nurse anesthetists (CRNAs) First responders: ex. EMTs, paramedics 	
	 Age >=18 years of age Provision of Informed Consent 	
Exclusion Criteria	 Active COVID-19 disease Confirmed prior COVID-19 disease Current fever, cough, shortness of breath Contraindication or allergy to chloroquine or hydroxychloroquine Prior retinal eye disease Known Chronic Kidney disease, Stage 4 or 5 or dialysis. Known glucose-6 phosphate dehydrogenase (G-6-PD) deficiency. Weight <40 kg Current use of hydroxychloroquine or cardiac medicines of flecainide, amiodarone, digoxin, procainamide, or propafenone Current use of medications with known significant drug-drug interactions: artemether, lumefantrine, mefloquine, tamoxifen, or methotrexate. 	

Statistical	 10% transmission rate for high-risk healthcare workers with		
Assumptions	no treatment		
	 Alpha = 0.025 (to account for two treatment groups vs. placebo comparisons) Assuming 15% lost to follow up in the placebo group and 5% lost to follow up in each treatment group N=3500 has 80% power to detect a hazard ratio of 0.65, using a two-sided log-rank test 		

Schematic of Study Design:

At the close of the study, any participant with ongoing illness will continue to be assessed for up to a total of 90 days after the common closing date.

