4.3.2 Randomization

- Participants will be randomized at the investigation pharmacy
- The investigational pharmacy will dispense masked study medicine (hydroxychloroquine or placebo)
- The study medicine will be shipped to participants to arrive ~1 day after enrollment
- 4.3.3 Day 1 Virtual visit
 - Verify receipt of study medicine
 - Clinical status check-in
 - Begins taking study medicine (2 tabs), then 2 tabs in 6-8 hours
 - Query for symptom status
 - Query for hospitalization or SAEs
- **4.3.4** Weekly Virtual visit
 - Clinical status check-in for COVID-19 symptoms
 - Assessment of adherence and side effects by self-report
 - Continue study medicine up to 12 weeks
 - Query for study medicine side effects since enrollment
 - Query for SARS-CoV-2 testing
 - Query for hospitalization or SAEs
- **4.3.5** Study termination virtual visit (to be completed on or shortly after the common closing date for the study)
 - Clinical status check-in for COVID-19 symptoms
 - Query for study medicine adherence and side effects since enrollment
 - Query for SARS-CoV-2 testing
 - Query for hospitalization or SAEs
 - Query for pregnancy status
 - Final outcome assessment
- **4.4** Individually identifiable health information: Name, date of birth, and phone number will be collected so as to prescribe study medication. Email addresses will be collected for communication. If participants are hospitalized, the hospitalization date will be collected.

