6.8 Enrollment/Baseline

- **6.8.1** Randomization (Day 0)
 - Participants will be randomized by a computer-generated algorithm using a permuted block randomization sequence
 - Investigational pharmacy will dispense the masked study medicine (12 week supply)
 - Study personnel will then courier study medicine to the participant
 - Participant will be sent an email to expect the medication to arrive the following day

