8.4 Type and Duration of Follow-up of Subjects after Adverse Events

Participants who are hospitalized for COVID-19 or SAEs will have up to 90 day follow up after the common closing date, to assess their final outcome. Management will be as per the participant's local healthcare provider.

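### The documents give incompatible durations for follow-up and dosing, so they do not settle whether routine safety contact covers the period in which participants take the drug

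*Combined protocol and SAP*

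**What the plan says.** **Follow-up.** The Summary (Duration of Participation) says "All patients will be followed for at least 4 weeks" and "Recruitment is expected to take 4 weeks, for a total study duration of 8 weeks", adding that the total depends on the enrolment rate. Section 2.2 repeats the 4-week recruitment period and 4-week minimum. Section 4.1 describes an event-driven trial: "Subjects will be followed until study termination". The termination visit in section 4.3.5 is "to be completed on or shortly after the common closing date for the study".

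**Dosing.** The Summary (Intervention Arms) gives the once-weekly arm "thereafter 400mg weekly for the duration of follow up, up to 12 weeks", and the twice-weekly arm is worded the same way. Section 2.2 mentions the 12-week maximum in connection with slower recruitment. Section 4.2 prescribes drug for up to 12 weeks. Section 6.8.1 says "Investigational pharmacy will dispense the masked study medicine (12 week supply".

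**Consent and other sections.** The comprehension check in section 13.3 includes "Duration of taking the study medicine (12 weeks", without the qualifier that 12 weeks is a maximum. Neighbouring items give the study duration as 90 days and the surveys as day 1 and then weekly. Section 14.4 times DSMB reviews by participants completing 90 days of follow-up. Appendix A places its second blood sample after 90 days of study drug and attributes that duration to the parent protocol.

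**After closing.** Sections 4 and 4.2 extend follow-up by up to 90 days for participants ill at the closing date. Section 8.4 says "Participants who are hospitalized for COVID-19 or SAEs will have up to 90 day follow up after the common closing date", and section 6.11 is similar for hospitalised workers with suspected COVID-19. Pregnant women are followed to the end of pregnancy (8.3.3). Section 6.12 gives everyone a contact email and a repeatable web form, with no stated end date.

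**The concern.** Routine questions on side effects, hospitalisation and SAEs run weekly and stop at the termination visit. On the expected schedule that visit falls 4 to 8 weeks after enrolment, so every participant still holds tablets, and the consent check has presented 12 weeks as the duration of treatment. The visible list for the termination visit asks about adherence and side effects since enrolment, but has no step that ends dosing or records leftover tablets. Accountability (6.4) is by self-report at weekly visits, which have by then ended.

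This matters because safety capture is already narrow. Section 8.2.1 does not capture adverse events unless they lead to hospitalisation, and section 8.3.1 relies on the hospitalisation-or-death endpoint to pick up relevant SAEs. If a participant who is well at closing has an event later, no planned question would elicit it. Participants may also have consented to a length of treatment and of surveillance that the operative sections do not guarantee.

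**Working it through.** **1. The plan's own timeline.** Recruitment of 4 weeks plus minimum follow-up of 4 weeks gives 4 + 4 = 8 weeks, as the Summary states. Individual follow-up therefore runs from 4 weeks (last enrolled) to 8 weeks (first enrolled). Nobody reaches 12 weeks or 90 days.

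**2. Dosing after the last routine contact.** Supply is 12 × 7 = 84 days (6.8.1). Days left = max(0, 84 − follow-up).

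| Reading | Follow-up | Dosing days after last routine contact |
|---|---|---|
| Consent wording, last enrolled | 28 | 56 of 84 (67%) |
| Consent wording, mean under uniform accrual (assumption) | 42 | 42 of 84 (50%) |
| Consent wording, first enrolled | 56 | 28 of 84 (33%) |
| Summary regimen text: dosing ends with follow-up | 28 to 56 | 0 |
| 90-day follow-up (13.3, 14.4) | 90 | 0 |

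If recruitment takes R weeks and the study closes 4 weeks later, follow-up runs from 4 to R + 4 weeks. The first enrolled reach 12 weeks only if R is at least 8. The last enrolled are still guaranteed only 4.

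**3. Drug remaining if dosing stops at closing.** Section 6.1.5 gives a half-life of 172 ± 39 h.

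- 172/24 = 7.17 days; (172 − 39)/24 = 5.54; (172 + 39)/24 = 8.79.
- Five half-lives, a reviewer's convention that is not in the documents: 5 × 7.17 = 35.8 days (27.7 to 44.0 for ±1 SD).

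For a participant closed at day 28, assume one compartment, complete and immediate absorption, both loading doses at time zero, and no dose on day 28. The share of total exposure falling after closing is then the amount in the body at day 28 divided by the total dose, with each dose decaying as 2^(−t/7.17).

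- Weekly: 800 mg on day 0 and 400 mg on days 7, 14 and 21, total 2000 mg. Remaining: 53.3 + 52.5 + 103.3 + 203.3 = 412 mg. 412/2000 = 20.6%.
- Twice weekly: 800 mg on day 0 and seven 400 mg doses at 3.5-day intervals, total 3600 mg. Remaining: 953 mg. 953/3600 = 26.5%.
- Over the ±1 SD half-lives: 14.5% to 26.4% weekly and 20.0% to 32.3% twice weekly.

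**4. Who is contacted after closing.** Active contact is described for participants who are ill, hospitalised or pregnant. For someone well at closing, only the participant-initiated routes in section 6.12 remain.

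**The case against.** A reader might infer that the plan prescribes up to 8 weeks of unmonitored dosing. The documents do not support that. The Summary ties dosing to follow-up, and section 2.2 presents the 12-week maximum as a provision for slow recruitment. The 12-week item in section 13.3 sits beside a 90-day study with weekly surveys, which would cover all 84 dosing days. The 67% arises only from pairing the consent wording with the 4-week minimum, and it applies to the last enrolled. This part of the objection stands: exposure without contact is a risk created by conflicting passages.

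Nor does all safety contact end at closing. Sections 6.11 and 8.4 do not limit the 90-day extension to people already in hospital on that date, and section 6.12 leaves a reporting route open. That also stands, but no routine question is planned that would identify a new hospitalisation in someone who was well, and section 6.12 depends on the participant taking the initiative.

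A reader might also infer that risk in the drug arms is understated. A common closing date falls alike on all randomised arms, and the documents give no event rate or onset pattern from which to derive a bias. The retinopathy and cardiomyopathy described in section 2.3.1 are tied to use beyond a year, so some extra weeks of contact would not detect them.

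The exposure fractions are approximate. With the stated Cmax of 1.2 nmol/mL, a single exponential implies an AUC of 1.2 × 172/ln 2, about 298 nmol·h/mL, against a stated AUC(last) of 75.4. The two agree only if sampling stopped near 72 h, which the documents do not say.

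Finally, the consent form, the study-schedule content and the design schematic were not available for this review, so an end-of-dosing instruction may exist there. Limited, hospitalisation-focused capture is also an open choice for a pragmatic trial. Neither point reconciles the stated durations.

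**Conclusion.** The point holds as a conflict between durations: a 4-week minimum, an 8-week expected total, a 12-week supply and consent item, and 90 days in sections 13.3 and 14.4 and Appendix A. Dosing after the last routine safety query is 33% to 67% of the 12 weeks if participants follow the consent wording on the expected schedule, and zero on the Summary regimen text or a 90-day follow-up. The documents do not settle which applies.

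Separately, if dosing stops at closing, about 36 days of washout (28 to 44) has no active contact for well participants, and about 21% (weekly) to 26.5% (twice weekly) of a 4-week participant's exposure falls in that period. These figures rest on the five-half-life convention and the one-compartment assumption respectively. The consequence for the safety endpoints is a loss of late events of unknown size. The primary efficacy analysis is not called into question here.

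**What to change.** - Reconcile the Summary (Intervention Arms and Duration of Participation) and sections 2.2, 4.1, 4.2, 4.3.5, 6.8.1, 13.3 and 14.4 with Appendix A on how long participants are followed and how long they take study drug, including when the closing date falls before 12 weeks. This review takes no position on which duration is right.
- Make the comprehension questions match the reconciled text.
- At the closing visit, record the date of the last dose and the number of tablets remaining.
- Keep the existing automated form (side effects, hospitalisation, SAEs) going to every participant until the reconciled end of dosing plus a post-dose window that the sponsor justifies from its stated half-life.
- Report events from that added period as safety data only, outside the primary time-to-event analysis.

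The cost is protocol and consent wording, a few more automated surveys, and a safety-data lock some weeks later. The primary analysis need not wait.
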